2.3. Study Design

This protocol describes refinement and pilot testing activities for the Injury Liaison Service outlined above. The following study designs will be employed:

- 1. Qualitative interviews** will be conducted with approximately 10 NH staff (i.e., nurse, certified nurse aide (CNA), physician, and nurse practitioner who have been employed in a nursing facility for at least 3 months) to gain a better understanding of effective and non-effective injury prevention strategies. Information from these interviews will be used to refine the program during co-design meetings with key stakeholders
- 2. A non-randomized pilot program in four nursing home facilities** will provide data on the implementation of the ILS Program. This includes cross-sectional measures of acceptability, demand, practicality, and feasibility obtained from the electronic medical record (EMR), the IP nurse, and a **post intervention survey** with approximately 60 staff across the four facilities. A **pre-post study design** will be employed in order to measure the safety and efficacy of the ILS Program. Safety and efficacy outcomes will be measured at the resident level.

2.4. Outcome measures. The list of measures, data source, and targets are summarized in Table 1 and described in detail below.

Table 1. Proposed Measures of Implementation, Efficacy, Safety, and Validity with Data Source and Target/Goal

Type	Outcomes	Data Source	Target/Goal
Implementation			
Acceptability	Family acceptance of recommendations	IP Nurse Tracking, staff survey	$\geq 50\%$
	Provider acceptance of recommendations		$\geq 50\%$
	Provider satisfaction		$\geq 80\%$
	Staff participation in virtual case based education program		10 staff/NH/mo.
Demand	Proportion eligible for intervention	IP Nurse Tracking	20%
	Proportion of high risk residents with deprescribing recommendations		50%
	Referral rates to virtual cased based education program		15%
Fidelity	Proportion of targeted staff completing intervention checklists	IP Nurse Tracking	90%
	Cost of IP Nurse per resident		\$225

Practicality	NH staff time	IP Nurse Tracking, staff survey, EMR	<2 hour/mo.	Acceptability: (Primary) Number of families that accepted one or more medication recommendation/ number of families offered a recommendation; Number of patients where
	High-risk Resident 6-mo attrition (death, leave NH)		<40%	
Fidelity/Safety				
Fidelity	No. of deprescribed medications at 3-6 months	EMR	≥1	
	Osteoporosis medication initiation		70%	

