Safety	Behaviors	MDS	<10% increase	
	Functional Decline			
	Unscheduled medical visits	EMR	≤2/facility	
Validation				
Outcome Measure	Injurious falls	MDS and Chart Review	>90% sensitive, >95% specific	

the provider accepted one or more recommendations / number of patients with a medication recommendation; % of staff that indicated they were satisfied or very satisfied with the ILS; proportion of staff that attended one or more virtual case based education sessions

(Secondary) number of total medication recommendations accepted/ total number of medication recommendations; proportion of staff that attended two or more virtual cased based education sessions.

Demand: We will use the FRAiL model to identify residents at greatest risk of injurious falls who are eligible for the ILS Program. Residents with an estimated 2-year risk of hip fracture of ≥5%, or similar target, will be considered high risk and eligible for the program. The facility staff will also be able to refer other at risk patients for participation in the program. Other demand outcomes include the proportion of high risk residents with one or more deprescribing recommendations or with a recommendation for osteoporosis treatment, AND referral rates to virtual case based education sessions, defined as the proportion of high risk residents discussed in these sessions.

Fidelity: At each facility, we will identify targeted staff including nurses and medical providers (physicians, nurse practitioners, or physician assistants) who will be asked to complete the program checklists. Our primary measure of fidelity will be the proportion of staff that complete ≥ 75% of requested checklists. As a secondary fidelity measure we will examine the proportion of resident checklists completed by a provider.

Practicality: We will estimate cost by monitoring the amount of time the IP nurse spends on each eligible resident. Other outcomes include the estimated amount of time the staff spend on the ILS service by self-reported survey AND the six-month attrition of eligible residents from the NH facility due to transfer, discharge to community, or death, as determined by the IP nurse from chart review.

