Fidelity: Fidelity will be measured as the average number of medications that were deprescribed at 1 and 4 months among high risk residents, as well as the proportion of high risk residents with a prescription for an osteoporosis medication at 1 and 4-months. The IP nurse will review the EMR to determine medications at 1 and 4 months after medication recommendations are finalized.

Safety: Detailed resident-level data collection includes the following potential adverse events related to medication changes: 1) escalating behaviors, worsening depression, or functional decline following psychoactive deprescribing; 2) unplanned medical visits for hypertension,

tachycardia, or hyperglycemia for cardiometabolic deprescribing; 3) new gastroesophageal reflux disease or esophagitis following bisphosphonate prescription.

Each facility will provide two Minimum Data Set (MDS) assessments following baseline in order to characterize the occurrence of these adverse events. Behaviors and depression will be measured using validated scales from the MDS.^{35,36} Any worsening of behavior (any category) as assessed by nursing will be considered. Worsening depression will be defined as a 1-point increase in the PHQ-9 or PHQ-9-OV. This corresponds with meaningful change in depression severity.³⁷ Any increase in the frequency of reported verbal, physical, or other behaviors will be considered. Functional decline will be defined as a 3-point increase in the MDS Activities of Daily Living Scale. A 3-point increase corresponds with complete loss of a single ADL or incremental loss of 2 ADLs.^{38,39} Change in depression, behaviors, and functional status will be measured using the MDS assessment closest to and preceding implementation and the subsequent MDS assessment.

Lastly The IP nurse will enter all targeted adverse events into the RedCap database. At the next study team meeting, or within 14 days, the IP nurse will review the event with the team for a determination of an adverse event using the validated Drug Withdrawal Probability Scale^{40,41} to determine if there is a probable, possible, or doubtful relationship between the medication change and the adverse event. Discordance will be adjudicated by a third investigator (physician).

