4.1. STUDY OBJECTIVES

Aim 1: *Develop an ILS care model designed to prevent injurious falls in NH residents using 1) an automated risk calculator to identify high risk residents, 2) centralized care coordination by an Injury Prevention Nurse, and 3) videoconferencing with NH staff.*

Aim 2: *Test implementation of the ILS in 4 NH facilities.* The intervention will target residents at high risk for injury as estimated by the risk calculator (~80 residents total). Results will be presented among all residents and in ADRD residents separately.

- **Aim 2a:** *Evaluate implementation* of the ILS including measures of acceptability, demand, fidelity, and practicality (e.g., provider and family acceptance of recommendations, staff participation and time.)
- **Aim 2b:** *Evaluate effectiveness and safety* of the ILS using change in process measures related to injurious falls (e.g., number of drugs prescribed, osteoporosis medication prescriptions, behaviors, and functional status). Process measures will be collected at baseline and 1 and 4 months post-intervention. Additional safety measures (e.g., unplanned medical visits due to hypertension or hyperglycemia) will be assessed at 1 and 4 months post-intervention by chart review.
- **Aim 2c:** *Validate the outcome measure for a future pragmatic clinical trial.* Injurious fall ascertainment from the MDS will be validated against chart review in the facilities.

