5.2.3. Resident exclusion criteria

1. Life expectancy < 6 months, as indicated by MDS assessment
2. Living in nursing home for less than 30 days
3. Proxy has communicated wish to opt-out of study

Residents *will not* be excluded from the study based on any specific diagnosis (e.g., congestive heart failure or schizophrenia); however, the algorithm used to make recommendations for medication management will consider individual co-morbidities. (see **Table 3** for details)

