Hypoglycemics – Sliding Scale Insulin (SSI)*	
 • Type II Diabetes, AND • SSI is the only insulin treatment, OR • SSI in addition to basal insulin, OR • SSI in addition to basal insulin and mealtime insulin 	
 • No taper needed • If most recent hemoglobin A1C <=8.5, discontinue SSI without adding treatment 	
 • 2 MDS assessments post intervention: MDS items pertaining to function (ADLs) • Chart review at 1 and 4 months post intervention: severe hyperglycemia (>400), polydipsia, polyuria, functional decline hospitalizations, ED visits 	
 • Nursing will measure fasting blood sugar daily for 2 weeks. Notify MD/NP for any BG >300 or >2 values over 200 (End date for this order is the same end date of the taper) 	
 • If most recent hemoglobin A1C >8.5, review average daily insulin requirement over prior 5–7 days, then initiate basal insulin at 50–75% of that average daily insulin requirement
		*Please see separate table for additional scenarios related to sliding scale insulin which deprescribing may be appropriate.			

Table 2. Algorithm for Prescribing Osteoporosis Treatment in NH-PRIDE study

Drug Class	Prescribing Criteria	Study Team will Monitor	Nursing will notify MD/NP for new symptoms	Treatment Options
Calcium and Vitamin D	
 • Life expectancy > 6 months based on MDS question J1400 or validated tool, and not enrolled in hospice, AND • No evidence of hypercalcemia (>10.5mg/dL) by chart review 	
 • 2 MDS assessments post intervention: MDS items pertaining to function (ADLs) • Chart review at 1 and 4 months post intervention: elevated serum calcium (>10.5mg/dL), worsening constipation, functional decline hospitalizations, ED visits 	
 • Nursing will notify MD/NP for worsening constipation 	
 • Ensure 1200mg calcium through diet and supplements. • 1000-2000IU vitamin D daily

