Antiresorptives	
 • Estimated FRAiL score \geq 10% OR Estimated FRAiL score \geq 5% + history of fracture • Life expectancy >6 months based on MDS question J1400 or validated tool, and not enrolled in hospice • No contraindications (allergy, etc.) 	
 • 2 MDS assessments post intervention: MDS items pertaining to function (ADLs) • Chart review at 1 and 4 months post intervention: gastroesophageal reflux, esophagitis, injection site reactions (for subcutaneous medications), hypocalcemia (<8.7mg/dL), functional decline, hospitalizations, ED visits 	
 • Nursing will assure proper administration of oral bisphosphonates (taken on empty stomach, sit upright for at least 30 minutes afterwards). • Nursing will notify MD/NP for worsening indigestion, injection site reactions (for subcutaneous medications) 	
 • Oral bisphosphonate • IV bisphosphonate • SQ denosumab

Table 3. Sliding Scale Insulin (adapt from Munshi et al. *Management of Diabetes in Long-term Care and Skilled Nursing Facilities: A Position Statement of the American Diabetes Association*. Diabetes Care. 2016)

Criteria	Schedule and Alternative Therapies
Scenarios in Which Deprescribing is a Focus	

 SSI is the only insulin treatment 	
 Discontinue (no taper necessary) If most recent hemoglobin A1C\leq8.5, discontinue SSI without adding treatment If most recent hemoglobin A1C$>$8.5, review average daily insulin requirement over prior 5–7 days, then initiate basal insulin at 50–75% of that average daily insulin requirement

 SSI is used in addition to scheduled basal insulin 	
 Discontinue SSI AND Add 50–75% of the average insulin requirement used as SSI to the current dose of basal insulin -- If postprandial hyperglycemia persists, add either fixed-dose mealtime insulin OR a non-insulin agent (preferably a dipeptidyl peptidase-4 inhibitor or other agent with low hypoglycemia risk)

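### Table 1 sets a 70% target for starting osteoporosis medication, but Section 2.4 counts any osteoporosis prescription, so residents treated at baseline who stay on treatment count toward it

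*Combined protocol and SAP*

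**What the plan says.** The Fidelity/Safety block of Table 1 lists "Osteoporosis medication initiation", with the EMR as source and a target of 70%. Section 2.4 says that the measures in Table 1 are described in detail in the text that follows. The second Fidelity paragraph there gives the measure as "the proportion of high risk residents with a prescription for an osteoporosis medication at 1 and 4-months". It does not require the prescription to be new, and it neither removes residents treated at baseline nor subtracts a baseline value.

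Four other places bear on the point:

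- Section 5.2.3 lists the resident exclusions: "Life expectancy < 6 months, as indicated by MDS assessment", a stay under 30 days, and proxy opt-out. Current osteoporosis treatment is not among them.
- Section 4.1, Aim 2b, plans to study "change in process measures related to injurious falls (e.g., number of drugs prescribed, osteoporosis medication prescriptions, behaviors, and functional status", and states that "Process measures will be collected at baseline and 1 and 4 months post-intervention".
- Section 7.3 has all prescribed medications abstracted from the chart at baseline, 1 month and 4 months.
- Section 10 says that the implementation measures, fidelity included, are described as defined in Table 1. It adds no definition of initiation.

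**The concern.** The label and the measure describe different quantities. Initiation is a count of new starts among people who could start. The text in Section 2.4 counts everyone with a prescription at follow-up, whenever it began. A resident who entered on treatment and stayed on it adds to the numerator although the program started nothing. If the program started no one, the reported figure would equal the share of residents already treated.

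At stake is what the pilot may say about one of its fidelity targets. A figure reported as initiation would mix existing users with new starts, and a reader comparing it with 70% could not tell them apart. The drugs that qualify are also not named for this outcome. Appendix 1, Table 2 places calcium and vitamin D in the osteoporosis algorithm alongside antiresorptives, and the size of the overlap with baseline treatment depends on which of these count.

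**Working it through.** The 70% is a goal without a stated derivation, so there is no figure of the plan's to reproduce. The interval in Section 10 concerns adherence to medication recommendations and is not an input here.

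**Inputs**

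- Expected high-risk residents: 80 (Section 2.6).
- Target: 70% (Table 1).
- Share treated at baseline, *b*: not given. Section 2.2 calls treatment rates very low. Assumed here: 5%, 10% and 20%, with 0% for reference.
- All baseline users are still on treatment at follow-up (assumed).

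**Formula**

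Let *i* be the share of untreated residents who start. The measure in Section 2.4 then reads

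measure = *b* + (1 − *b*) × *i*.

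Setting this to 0.70 gives *i* = (0.70 − *b*) / (1 − *b*). In counts, the target is 0.70 × 80 = 56 residents with a prescription.

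| Treated at baseline (assumed) | New starts needed | Untreated residents | Initiation that meets the target | Gap to 70% |
|---|---|---|---|---|
| 0 of 80 (0%) | 56 | 80 | 70.0% | 0 points |
| 4 of 80 (5%) | 56 − 4 = 52 | 76 | 52/76 = 68.4% | 1.6 points |
| 8 of 80 (10%) | 56 − 8 = 48 | 72 | 48/72 = 66.7% | 3.3 points |
| 16 of 80 (20%) | 56 − 16 = 40 | 64 | 40/64 = 62.5% | 7.5 points |

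Conversely, if exactly 70% of untreated residents started, the measure would read 0.05 + 0.95 × 0.70 = 71.5% at *b* = 5%, and 0.20 + 0.80 × 0.70 = 76% at *b* = 20%.

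**Continuation**

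If only a share *c* of baseline users still has a prescription, *i* = (0.70 − *c* × *b*) / (1 − *b*). At *c* = 0.70 this equals 0.70 for any *b*. The prevalence definition therefore eases the target only when more than 70% of baseline users continue. Below that share, the definition makes the target harder to meet.

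**Calcium and vitamin D**

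If these count, *b* is the share already on any of the listed drugs. The documents give nothing from which to set it, so the 5% to 20% range has no basis on that reading and no size is offered.

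**The case against.** The strongest reply is that the rest of the plan already supplies the baseline. Aim 2b looks at change in osteoporosis prescriptions, medications are abstracted at baseline, and Section 10 points back to the wording of Table 1, which does say initiation. An analyst could read these together and count new starts. This stands in part: the data exist, and the baseline rate would be visible beside the follow-up rate. But none of these places defines initiation or ties the 70% to new starts, and the only operational text counts any prescription.

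A second reply is that Section 6.3 limits the follow-up review to residents with a finalized medication recommendation. That does not remove the overlap. A treated resident with only a deprescribing recommendation is still reviewed and still counts.

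A third reply is that the effect is small. This largely stands. At 5% the gap is 1.6 points, against a 95% half-width of 1.96 × √(0.70 × 0.30 / 80) = 10.0 points for 70% of 80. Full continuation is also an assumption: residents leave or die, and Section 8.2 foresees that some antiresorptive treatment ends.

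A reader might go further and infer that 70% is out of reach, because the antiresorptive criteria in Appendix 1, Table 2 are narrower than program eligibility. The documents do not support that. They do not say that only antiresorptives count, and they do not give the share of residents who meet those criteria.

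**Conclusion.** The mismatch holds: the target is named for initiation, and the measure counts any prescription at follow-up. With 80 residents, an assumed 5% to 20% treated at baseline and all of them continuing, the target would be met with initiation in 68.4% to 62.5% of untreated residents, which is 1.6 to 7.5 points under its face value. The size is small if baseline treatment is as low as Section 2.2 suggests, and unknown if calcium and vitamin D count.

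The consequence is limited to whether a descriptive pilot target is judged met. A reader might infer that the pilot's precision or its decisions are compromised. Section 10 plans no statistical testing, names only acceptance of recommendations as the trigger for refining the program, and will not power the future trial on these results. Nor does the point carry over to the deprescribing row of Table 1. The 4-month review lies within that row's 3 to 6 months, and what remains open there is mostly missing detail.

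**What to change.** In Table 1 and the second Fidelity paragraph of Section 2.4:

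1. Score the 70% target as the proportion with a new osteoporosis prescription at follow-up among high-risk residents who had none at baseline.
2. Keep the proportion with any osteoporosis prescription as the Aim 2b before-and-after measure, reported beside its baseline value.
3. State which drugs count, and report antiresorptives and calcium/vitamin D separately.
4. Confirm that 70% is still the intended goal for the new denominator, or restate it.

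The result among residents with an osteoporosis recommendation may be shown as a supplement. It should not be the denominator of the target: it overlaps the acceptance measures in Section 2.4 and would drop residents to whom the service should have made a recommendation but did not.

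The cost is wording only, since medications at baseline, 1 month and 4 months are already collected. The denominator falls from 80 to about 76 to 64 under the assumed range. By the normal approximation, the 95% half-width at 70% goes from 10.0 points to 1.96 × √(0.21/76) = 10.3 points, or 1.96 × √(0.21/64) = 11.2 points.

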2.5. ILS Program Description

All four facilities will receive the same ILS Program. Each facility will participate for a total of 18 months, including a 6-month start-up/planning period, a 6 month implementation period, and a 6 month data collection period. Residents eligible for the ILS Program will be identified during the 6-month implementation period, and each resident will be followed for up to 6 months.

The ILS Program has three main components (**Section 6** provides additional detail):

1. Automated identification of NH residents at high risk for injurious falls. Our IT personnel will work with the IT Departments at each of the 4 NH facilities in order to program the automated calculation of the FRAiL model from the EMR/MDS repository. Residents with an estimated FRAiL score $\geq 5\%$ are eligible for the medication review via the IP nurse and videoconferencing. The facility staff may also suggest other residents for participation.
2. The IP nurse will provide recommendations to manage medications. The IP nurse will be supported by an interdisciplinary team including geriatricians, bone health experts, ADRD behavior management experts, nursing, and pharmacist. The IP nurse will develop an Injury Prevention Plan (IPP) with recommendations for medication changes including deprescribing medications association with falls and a prescription for osteoporosis medications. Recommendations will be left for the primary providers to review and co-sign.
3. Virtual case based education sessions to educate staff. We will hold regularly scheduled (up to monthly) virtual case based education with our interdisciplinary team and staff (nurses, CNAs, and providers) from the 4 NH facilities. During the conferences we may review some of the residents from each facility who are at high risk for injurious falls. These sessions could also include educational material on non-pharmacologic strategies to manage dementia with behaviors, falls prevention, deprescribing, and osteoporosis management. Frequency of meetings and content of the meetings will be individualized to each facility needs regarding case review,

education, or other implementation support needs.

2.6. Sample Size and Population

We anticipate enrolling approximately 10 NH staff and 10 patient/families for an interview on injury prevention.

We anticipate approximately 20% of long-stay residents at the 4 facilities will be eligible for the medication management program (n=80). See **Section 10, Statistical Considerations** for a full explanation of sample size.

We anticipate conducting interviews to assess the acceptability and practicality of the ILS Program on 60 staff members across the four facilities.

4. PARTICIPATING STUDY SITES

The study is being conducted at 4 NH facilities: two in the Durham, NC area and two in the Boston area. Eligible homes must have at least 80 long stay beds. Recruitment and study enrollment will be done in 2 waves, with each wave starting three months apart. In each wave, 2 NHs will begin the study.

For specific Aim 2c, the validation of the outcome measure injurious falls via the MDS v3.0, it will take place at one NC facility and Hebrew SeniorLife.

